#### IV. SUBJECT ENROLLMENT

#### **Recruitment Methods**

Participants will be recruited from multiple sources:

#### MGB Biobank (IRB Protocol 2009P002312)

The MGBB maintains plasma, serum, and DNA samples from tens of thousands of patients who have given their consent for broad-based research. Subjects consent to allow storage of up to fifty milliliters of blood, linkage of the sample with their MGB electronic medical record, and storage of a health information questionnaire that collects additional information about health behaviors, lifestyle, and family history. Subjects also provide consent to be re-contacted by the MGBB in the future for additional information/samples, and to be asked if they would be interested in joining other research studies. All samples and linked information stored in the Mass General Brigham Biobank are accessible for broad research use by Mass General Brigham investigators.

In order to identify eligible candidates for this study, we may conduct fully identified chart reviews, RPDR queries, and queries in the Biobank Portal. The MGB Biobank will send an invitation letter, co-signed by the Biobank PI and our PI, and opt-in or opt-out letter to candidates. The Biobank will also provide us with an identified data set that includes patient MRNs, names, and contact information for all re-contacted patients. At least ten business days after the Biobank sends the recontact letters to patients, we will call each candidate on the list (who did not choose to opt-out) to invite them to participate in our study. Upon request, we may provide the Biobank with a list of the response status for each patient so that the Biobank may measure the success rate for the re-contact process.

# Individuals Seeking Care in the Reproductive Endocrine Associates (REA) Clinic

We will review identifiable medical records to determine if patients are candidates for study participation. Candidates may be introduced to the study by their REA physician (via phone, email, letter, virtual visit or in-person) and will be recruited to the study by other study team members.

#### Referrals from Non-REA Clinical Providers

Clinical providers both inside and outside of MGB may introduce subjects to this study. With permission from the referred individual, the provider can share the candidate's contact

information with the study team to proceed with recruitment. We will review medical records to determine if these patients are potential candidates for study participation.

#### Other Reproductive Endocrine Unit (REU) Studies

We will review identifiable records of individuals who previously participated or expressed interest in other research studies in the REU. The study team may contact candidates (via phone, email, letter, or in-person) who have agreed to be contacted about future studies.

- A. If these individuals have an established clinical relationship with any physician investigator on this study, that physician may introduce the study, and recruitment of that candidate will be led by other study team members.
- B. If these potential subjects do not have a clinical relationship with one of the physician investigators, they will first be contacted via letter. Individuals who express interest in the study following the recruitment letter will be contacted by the study staff and recruited under guidance of MGB policies. At least ten business days after the letter is sent, we may call each individual (who did not choose to opt-out) to ask whether they would like to participate in our study.

#### **Pre-Screening**

Individuals recruited from MGB sources may have medical records reviewed for eligibility. In order to assess eligibility of all individuals, we may ask pre-screening questions via telephone or REDCap, and may request clinical notes and/or endocrine labs from their endocrinologist, PCP, or other health care provider. If outside records are requested, candidates will be asked to complete medical record release forms. Identifiable information on individuals who do not enroll may be retained but will not be linked to any collected health information without permission of the individual.

#### Consent

Consent may be obtained either in person (at Massachusetts General Hospital) or remotely. The consent form is provided for the subject to review prior to the consent process and study participation. Informed consent will be obtained by a licensed physician investigator or by non-physician investigators who are nurse practitioners or physician assistants with backup by a licensed physician.

The consent process will take place prior to the commencement of study procedures and will in all instances include a complete explanation of the study by one of the study medical professionals (physicians, physician assistants, or nurse practitioners). Study staff will go over the purpose of the study, study procedures, potential risks of participation, and alternatives to participation. Before signing an MGB HRC-approved consent form, potential participants will be given the opportunity to ask the study investigators any questions that they may have concerning the study. The voluntary nature of participation in these studies will be emphasized. It will be made clear that a decision not to participate will in no way affect the relationship of patient to physician, investigator, or institution regarding the ongoing provision of care. Finally, a copy of the signed consent form, containing all the information outlined above, as well as contact information for the principal investigator will be provided to the study participant in person, via mail, or electronically.

When consent is obtained in person, after all parts of the consent discussion are completed, the subject will sign the consent form in the presence of the study investigator. The study investigator will also sign the consent form at this time.

When consent is obtained remotely, the study investigator will complete the consent process, as described above, over the phone. The study investigator will confirm the subject's identity before signature is obtained. The subject and study investigator will sign the consent form at this time.

REDCap eConsent will be used for all signatures. All electronic logging information and an electronic copy of the consent will be automatically saved by REDCap. Subjects may complete electronic signatures using either their own device or a research-owned iPad.

If the individual's preferred language is not English, it is at investigator discretion to determine if participation is appropriate and raises no safety concerns due to potential communication difficulty. If the individual does participate, in accordance with MGB policy, we will work with a remote or in-person interpreter to ensure the consent form can be presented to the subject in their preferred language. The subject will sign a full consent form translated into that language.

#### V. STUDY PROCEDURES

#### **General Outline of Protocol**

The goal of these studies is to assess the GnRH response to kisspeptin individuals carrying genetic variants of interest. GnRH cannot be measured in the peripheral circulation, and so LH will be measured as a surrogate marker of GnRH secretion. LH is secreted by the pituitary in direct response to GnRH, and there is a well-established one-to-one concordance between GnRH and LH pulses. 

The protocol will consist of up to 2 visits:

- A screening visit
- A visit at the MGH Translational and Clinical Research Centers (TCRC) or REU to assess the subject's LH pulses and response to kisspeptin

The total amount of blood drawn across all parts of the study will not exceed MGB IRB quidelines.

#### **Protocol Details**

#### 1. Screening:

Screening procedures will include a complete medical history, physical examination (including a breast exam for female subjects), and laboratory blood tests to ensure subjects meet the inclusion criteria. The total volume of blood drawn during screening is approximately 20 mL.

Screening laboratory tests

- Reproductive hormones including, but not limited to: luteinizing hormone, follicle stimulating hormone, progesterone, estradiol, testosterone
- Hemoglobin (with study medical professional approval, can be based on lab result from medical record, within past 6 months)
- hCG serum pregnancy test (only women who can get pregnant)

All components of screening may be performed at the MGH REU or remotely. Therefore, some participants might not need an in-person screening visit at MGH.

• The screening medical history may be obtained by phone.

- Documentation of a physical examination performed by a non-study physician within the previous 12 months may be used in lieu of an in-person physical examination to determine eligibility.
  - All participants will undergo a physical examination by a study investigator prior to frequent blood sampling.
- If non-MGB medical records will be obtained for documentation of eligibility, subjects will complete an MGH medical record release form.
- If applicable, remote screening laboratory tests will be performed at a local laboratory site (e.g., Quest Diagnostics, etc.); study funds will pay for all phlebotomy and shipping costs.

If all eligibility criteria are met, a member of the study team will contact the subject to schedule the study visits.

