#### **Inclusion Criteria**

#### All subjects will meet the following criteria

#### History:

- genetic variant(s) predicted to be linked to reproductive axis (dys)function
- all medical conditions stable and well controlled
- for men
  - o age 18-60 years
- for women
  - o age 18-40 years
- no condition (medical, mental, or behavioral) that, in the opinion of a study investigator, would likely interfere with participation in/completion of the protocol
- no current or recent use of a medication (including hormonal replacement) that, in the
  opinion of a study investigator, can modulate the reproductive axis or willing to complete
  an appropriate washout for that particular medication and its method of administration no
  active illicit drug use
  - any active use of marijuana will be evaluated by a study medical professional to determine if it may impact study participation; individuals who regularly use marijuana may be asked to washout as referenced in the medication washout section below
- no excessive alcohol consumption (< 10 drinks/week)

- for women
  - not breastfeeding
  - not pregnant
- if applicable, willing to use birth control methods (as approved by a study medical professional) during the entire study

Physical examination:

- normal blood pressure, (systolic BP < 140 mm Hg, diastolic < 90 mm Hg) Laboratory studies:
  - for women
    - negative serum hCG pregnancy test at the time of screening (additional urine pregnancy test will be conducted prior to drug administration)
  - · hemoglobin within sex-specific reference range

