#### VII. RISKS AND DISCOMFORTS

#### Blood Draws and IV Lines:

There is a slight discomfort associated with the placement of IV lines and a small risk of infection at blood draw sites. There is a slight chance that an IV line placed will fail. In the event this occurs, a new IV line will be placed. Subjects may faint from blood drawing or develop bruise or irritation at the site of the blood draw. In addition, it is possible that subjects could develop anemia from blood-drawing. Subjects will be instructed to avoid donating blood or having large blood draws for 8 weeks before and after the study.

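### With a study clinician's approval, a chart hemoglobin up to 6 months old can qualify a participant for a visit that draws about 216–365 mL, and no repeat is required

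*Combined protocol and SAP*

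**What the plan says.** Under Inclusion Criteria, the laboratory requirements include "hemoglobin within sex-specific reference range", with no date attached to the test.

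Under 1. Screening, hemoglobin is one of the listed blood tests. It alone carries an alternative: "with study medical professional approval, can be based on lab result from medical record, within past 6 months". The reproductive hormones on the same list have no chart alternative, so blood is taken at screening in any case. On volume: "The total volume of blood drawn during screening is approximately 20 mL". For draws made at a local laboratory, "study funds will pay for all phlebotomy and shipping costs".

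Under 3. TCRC Visit, samples of 3–5 mL are taken every 10 minutes for 12 hours, with a ceiling of 550 mL. The checks described there are a urine pregnancy test for women (those surgically sterilized excepted) and vital signs. Hemoglobin is neither among them nor among the halting criteria.

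Under Blood Draws and IV Lines, the protocol names anemia as a possible result of the blood drawing and states: "Subjects will be instructed to avoid donating blood or having large blood draws for 8 weeks before and after the study". It does not say when that instruction is given.

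**The concern.** The hemoglobin criterion is the plan's only laboratory check against a harm that the plan itself names. A result that predates a blood loss cannot do that job.

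The plan renews comparable screening evidence. The serum pregnancy test is followed up: an "additional urine pregnancy test will be conducted prior to drug administration". An outside physical examination up to 12 months old can support eligibility, but a study investigator must still examine every participant before sampling. A chart hemoglobin has no such follow-up.

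The 8-week restriction fills only part of the space. It is worded as an instruction, so by itself it cannot prevent a loss that happened before it was given, and no eligibility criterion excludes a recent donor. The volume limits do not help here: one covers "The total amount of blood drawn across all parts of the study" and the other the visits, so neither counts blood lost elsewhere. At stake is the safety of a participant who, by the protocol's own account, gains no direct benefit from taking part.

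**Working it through.** The protocol states no figure for the scheduled volume, only the ceiling, so there is none to reproduce. The check is direct arithmetic.

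**Volume drawn at the visit** (inputs from 3. TCRC Visit)
- Intervals: 12 h × 60 / 10 = 72. That is 72 draws, or 73 if a time-0 sample is taken; the protocol does not say which.
- 72 draws: 72 × 3 = 216 mL to 72 × 5 = 360 mL.
- 73 draws: 73 × 3 = 219 mL to 73 × 5 = 365 mL.
- Range over both counts: 216–365 mL. With the roughly 20 mL taken at screening: 236–385 mL.
- All of these are below 550 mL, so no limit is breached.

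**Age of the qualifying value at the visit** (inputs from 1. Screening and the washout list)
- 6 months = 6 × 365.25 / 12 / 7 = 26.1 weeks.
- The protocol does not say from which date the 6 months is counted. If it is counted back from the visit, 26.1 weeks is the maximum.
- If it is counted back from screening and an oral contraceptive washout (more than 8 weeks) follows, a value at the limit is more than 26.1 + 8 = 34.1 weeks old at sampling.

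**Reach of the 8-week instruction** (input from Blood Draws and IV Lines)

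Let t be the weeks from instruction to visit. The part of the 8-week window already past when the instruction is given is max(0, 8 − t). The documents do not give t, so it is shown as a range.

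| t (weeks) | Weeks of the window already past |
|---|---|
| 0 | 8 |
| 2 | 6 |
| 4 | 4 |
| 6 | 2 |
| 8 or more | 0 |

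A participant with no washout, or with one of those listed at more than 2 weeks, may be near the top of this table. A washout of more than 8 weeks begun after the instruction closes the donation gap, but it also makes the chart value older.

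**Sequence that the written rules allow:** normal chart value; donation; screening and instruction; visit less than 8 weeks after the donation. No written eligibility criterion or visit check would stop it, although clinical judgment might.

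**The case against.** The strongest reply is that testing at screening is the default. The chart value is an exception that a clinician must approve, and that clinician can refuse an old value or one followed by blood loss. A complete medical history is taken, and an investigator examines everyone before sampling. Records of earlier participants in the unit's other studies are reviewed. Eligibility is followed by a contact in which "a member of the study team will contact the subject to schedule the study visits", so the date can be set to respect the 8 weeks. Saline replacement, vital signs at least every 4 hours and the volume ceiling add protection. The consent form is not in the reviewed copy and may contain a donation instruction or question. Harm would need the exception to be used, a loss to fall in the gap, and the history, approval and examination all to miss it.

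Most of this stands, and it is why the point is minor. It does not remove the point. The history may be taken by phone and no donation question is specified. An examination is not a hemoglobin test. Saline replaces volume, not red cells.

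Three stronger readings are tempting, and the documents support none of them:
- A reader might infer that the whole stretch of the 6 months lying before the 8-week window is a period of exposure. A loss that early complies with the protocol's own 8-week restriction, so that stretch does not measure harm.
- A reader might infer that a known recent donor would be sampled anyway. The protocol does not say so, and its window can be honored when the visit is booked.
- A reader might infer that the sampling volume is itself excessive. It is within the stated ceiling, and the documents give no threshold that it exceeds.

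**Conclusion.** The point holds as a minor participant-safety improvement. The approved exception lets a value of up to 6 months stand, unrepeated, as the hemoglobin evidence for this sampling. That value may no longer describe the participant on the day.

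The donation example assumes a loss after the chart test and before the instruction, with an instruction-to-visit interval shorter than 8 weeks. The text leaves that sequence open without stating that it occurs. The figure of more than 34 weeks depends on counting the 6 months from screening. Neither the frequency of such a loss nor the fall in hemoglobin can be estimated from the documents, and the existing clinical review makes harm unlikely. Sample size, power and analysis are not affected.

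**What to change.** Delete the chart alternative under 1. Screening and run hemoglobin on the blood already drawn there for the hormones. If the alternative is kept, accept a chart value only when the participant confirms no donation or large draw since its date, and otherwise test. Either change makes the qualifying result postdate any loss before screening that the participant knows of. Further questions at scheduling or on the visit day can be left to the visit checklist.

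The cost is one routine test for each participant who would otherwise have used a chart value. No additional visit is needed, and remote draws are already paid for. An occasional participant may be deferred if the new result is out of range.

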## 2. Pre-Study Visit Interventions

Subjects may undergo these interventions prior to either or both visits to the TCRC or REU.

# Sex Steroid and Medication Discontinuation ("Washout")

Subjects on hormonal medication (including oral contraceptives or hormone replacement) or non-hormonal medication that may modulate the reproductive axis may be asked to undergo a washout period appropriate to that particular medication and its method of administration as follows:

- Pulsatile GnRH therapy > 2 weeks
- Gonadotropin injections > 4 weeks
- Transdermal testosterone > 2 weeks
- Testosterone injections > 6 weeks
- Oral contraceptive pills > 8 weeks
- Oral, vaginal, or transdermal estrogen (physiologic dosing) > 2 weeks
- Oral or vaginal progestin (physiologic dosing) > 2 weeks
- If not specified above, a length of time > 5 half-lives of the drug

Subjects will be advised to discuss the washout with their prescribing physician prior to beginning washout. Any subject who experiences intolerable side effects as a result of medication washout will end participation in the study and be instructed to follow recommendations by their prescribing physician regarding resuming any medications.

#### 3. TCRC Visit:

The general structure of these visits is:

- a period of q10 minute blood sampling without intervention to assess endogenous hormone secretion,
- administration of kisspeptin followed by q10 minute blood sampling to assess the response to kisspeptin, and
- administration of GnRH followed by q10 minute blood sampling to assess the response to GnRH.

These may include the following procedures:

Female subjects will undergo a urine pregnancy test. The results of the pregnancy test
will return prior to any study drug administration and a positive pregnancy test will result
in immediate termination of the study.

- Female subjects with any well-documented method of surgical sterilization will not undergo a pregnancy test
- Frequent blood draws (3-5 mL) every 10 minutes for 12 hours; such that the total amount of blood drawn during the visits does not exceed 550 mL
- Kisspeptin administration of one IV bolus at hour 8
  - o The dose of the kisspeptin bolus will not exceed 13.19 mcg/kg (10 nmol/kg)
- GnRH administration of one IV bolus at hour 11
  - o The dose of the single GnRH bolus will be in the range of 25-75 ng/kg
- EMLA cream may be used to ease discomfort from needle insertion.

Subjects will receive isovolumetric replacement with saline during blood sampling. Kisspeptin will be administered by a TCRC RN or study medical professional. Vital signs (HR, BP, RR, and T) will be measured prior to beginning frequent sampling and at least once every 4 hours during sampling.

Study procedures will be halted if any of the following criteria are met at any point in the study.

- Blood pressure > 180 mmHg systolic or >105 mmHg diastolic at any point during the protocol
- Development or suspicion of an allergic reaction or serious adverse reaction
- Positive pregnancy test
- Temperature ≥101.5°F

Any subject who develops high blood pressure or an allergic reaction will receive medical care until the issue is resolved, with subsequent follow-up as needed.

#### **Additional Study Procedure Information**

#### Source, Preparation, and Storage of Kisspeptin

GMP-grade kisspeptin 112-121 powder and GMP-grade GnRH powder are synthesized by Polypeptide Laboratories (San Diego, CA). MGH Clinical Trials Pharmacy (CTP) receives and maintains the powder, reconstitutes powder into solution for use, and stores the solution. Each new batch of solution is sent for sterility (bacteria/fungi) testing at ARL Bio Pharma (Oklahoma City, OK), endotoxin testing at Dynalabs, LCC (Saint Louis, MO), and concentration testing at AAA Service Laboratory (Damascus, OR). We have previously found that the batches of kisspeptin and GnRH maintained sterility and stable concentration for at least 12 months. Each batch of kisspeptin or GnRH solution is given an expiration based on MGH CTP policy.

Prior to kisspeptin administration, a member of the study team will calculate the amount of kisspeptin that the participant will receive. The orders are sent to MGH CTP who double check the weight-based dose. MGH CTP prepares each participant's dose in accordance with MGH CTP guidelines. Study staff pick up the drug from pharmacy and bring it to the REU or the TCRC. Once there, the drug is logged in and dose, name, and date of birth are checked by study staff and, if applicable, TCRC staff. The drug is stored in a locked location until use.

#### **Justification of Doses**

The bolus dose of kisspeptin to be given will not exceed 13.1 mcg/kg = 10 nmol/kg, which
is equal to the largest IV dose of kisspeptin 112-121 used in human studies in the literature
to date.

 GnRH doses of 25-75 ng/kg give LH responses in the physiological range in most subjects. Under protocols in the Reproductive Endocrine Unit, subjects have been given GnRH at doses up to 800 ng/kg every 2 hours for up to 12 months with no significant adverse effects.

